### 7.3.2 Packaging and Labeling

Subjects will receive a total of 14 syringes of study drug or placebo and 14-unit dose containers of albuterol (plus 2 extras in the event of breakage) for each treatment period.

Each kit with syringe of study drug or placebo and the albuterol ampule will be labeled with the required FDA warning statement, the study ID, protocol number, the name of the sponsors, and directions for patient use and storage.

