	
bronchodilator reversibility is <12% in these participants, a diagnosis of asthma acceptable to the investigator is sufficient for inclusion in ENACT.
 
5. Clinical history of asthma per patient report or medical record
 
6. Pre-bronchodilator FEV1 > 35% predicted
 
7. Post-bronchodilator FEV1 > 40% but < 90% predicted. If the participant has past evidence of mucus impaction as described by a radiologist on a prior chest CT scan, then post-bronchodilator FEV1 needs to be >40% but <95% predicted.
 
8. Asthma requiring treatment with inhaled corticosteroids (ICS) for 3 months or greater.
 
9. CT mucus score <math>\geq 5</math>
 
10. Ability to tolerate study drug reflected by a post-treatment FEV1 <math>\geq 80\%</math> of pre- treatment, pre-bronchodilator FEV1
 
Exclusion Criteria
 
1. Pregnant, breastfeeding, or unwilling to practice birth control during participation in the study
 
2. Presence of a condition or abnormality that in the opinion of the Investigator would compromise the safety of the patient or the quality of the data
 
3. Smoking of tobacco or other recreational inhalants in last year and/or >10 pack-year smoking history
 
4. Current participation in an investigational drug trial
 
5. Uncontrolled asthma as evidenced by an asthma exacerbation in 6 weeks prior to study participation or albuterol use greater than 8 puffs per day
 
6. Other chronic pulmonary disorders, including (but not limited to) cystic fibrosis, chronic obstructive pulmonary disease, chronic bronchitis, vocal cord dysfunction (that is the sole cause of respiratory symptoms and at the PI's discretion), severe scoliosis or chest wall deformities that affect lung function, or congenital disorders of the lungs or airways
 
7. Unwillingness to follow study procedures
 
8. History of allergy or intolerance to study drug
 
9. Any other criteria that places the subject at unnecessary risk according to the judgment of the Principal Investigator

TEST PRODUCT, DOSE, AND ROUTE OF ADMINISTRATION	
10% NAC (3 ml) and 2.5 mg albuterol (0.5 ml)
 
Product will be administered every 8-12 hours (2 times per day) for 14 days. Medication will be administered via a portable nebulizer.

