### 7.3.1 Formulation of Test Product

10% NAC is an existing formulation of Mucomyst (Mucomyst-20), manufactured by American Regent, for aerosol administration in the management of patients with chronic bronchopulmonary disease. 10% NAC is a colorless solution that requires no reconstitution.

Albuterol sulfate inhalation solution is an existing formulation of Proventil Nebules, manufactured by Nephron Pharmaceuticals Corporation for oral inhalation in the management of patients with bronchospasm. Albuterol sulfate inhalation solution is a clear, colorless solution.

Table 1: Formulation and Measured pH of 10% NAC, control product and albuterol

	10% NAC	0.9% Saline	Albuterol
Active Ingredient, mg/mL	Acetylcysteine 100mg/mL		Albuterol sulfate 2.5 mg/0.5mL
Other ingredient, mg/mL	Edetate disodium, sodium hydroxide, purified water	Sodium chloride Purified water	Water, sodium chloride, sulfuric acid
pH	7	5.7	3-5

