### 7.4.1 Dosage/Dosage Regimen

During each treatment period participants will nebulize one syringe of study drug and one unit dose container of albuterol using a portable nebulizer. Participants will be instructed to take two doses per day, spaced at approximately 8-12 hour intervals. No adjustments will be made based on weight or age.

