## **7.5 Supply of Study Drug at the Site**

Study drug supply will be maintained by MAPRx and will be supplied on a per participant basis. 7-day study drug supplies will be delivered to the clinical site within 48 hours of study visit corresponding to the start of week one of the treatment period and week two of the treatment period.

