### 14.3 Analysis of Primary Endpoint

The primary analysis is a paired t-test analysis of the % change in FEV1 from the start to the end of the two-week treatment period with two times daily NAC (Mucomyst-10). The secondary analysis will be to determine how the change in FEV1 relates to the change in CT mucus score.

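### Section 7.3.2 states 14 syringes and 14 albuterol units per treatment period, where the regimen in the synopsis, 4.1 and 7.4.1 implies 28 of each; 14 is probably a weekly count labelled as a period total.

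*Combined protocol and SAP*

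**What the plan says.** **Supply count.** Section 7.3.2 states: "Subjects will receive a total of 14 syringes of study drug or placebo and 14-unit dose containers of albuterol". The sentence continues "plus 2 extras in the event of breakage) for each treatment period", so the count is given as a total for the period.

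**Regimen.** The synopsis states, for the test product: "Product will be administered every 8-12 hours (2 times per day) for 14 days". It gives the same frequency and duration for the control, and Section 4.1 repeats them. Section 7.4.1 adds the use per dose, "participants will nebulize one syringe of study drug and one unit dose container of albuterol using a portable nebulizer", and the daily frequency: "Participants will be instructed to take two doses per day, spaced at approximately 8-12 hour intervals".

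**Delivery and dispensing.** Section 7.5 states: "7-day study drug supplies will be delivered to the clinical site within 48 hours of study visit", and ties these deliveries to the starts of week one and week two of the treatment period. Section 7.6 has participants return after the first seven days and collect the second seven days of drug. The Visit 5 list dispenses a further seven days of drug (subject to adherence) in the first period, and the Visit 9 list does so in the second period.

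**Supervised doses.** Section 5.3 has the first two doses of each period given in the clinic.

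**Product name.** Section 7.3.1 says "10% NAC is an existing formulation of Mucomyst (Mucomyst-20". Section 14.3 refers to "two times daily NAC (Mucomyst-10". Table 1 gives the concentration as 100 mg/mL.

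**The concern.** Section 7.3.2 is an operational section, and its count cannot be obtained from the regimen stated elsewhere. Someone who took the period total at face value would plan for about half of the doses. The primary endpoint is the percentage change in FEV1 from the start to the end of the treatment period. If supply did follow that line, the end-of-period measurement would reflect about half of the exposure that the protocol describes.

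The sections also do not combine cleanly. Read with Section 7.5, a period total of 14 could mean two deliveries of seven syringes. Read as a weekly figure, it means two deliveries of 14. The text does not say which section governs.

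**Working it through.** **Inputs**

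- Syringes and albuterol units per dose: 1 of each (Section 7.4.1).
- Doses per day: 2 (synopsis, 4.1, 7.4.1). Cross-check: Section 11.1 and the Early Withdrawal Visit list set five treatment days beside 10 treatments, and 10/5 = 2 per day.
- Days per treatment period: 14 (synopsis, 4.1).
- Stated supply per period: 14, plus 2 extras (7.3.2).
- Doses given in the clinic per period: 2 (5.3).

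**Step 1. Try to reproduce the stated figure of 14**

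Units per period = units per dose x doses per day x days = 1 x 2 x 14 = 28. This does not reproduce 14.

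**Step 2. Allow for the extras and the supervised doses**

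If the supervised doses are supplied separately, the doses left are 28 - 2 = 26.

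| Supply counted | Doses to cover | Share covered |
|---|---|---|
| 14 | 28 | 14/28 = 50% |
| 16 (with extras) | 28 | 16/28 = 57% |
| 14 | 26 | 14/26 = 54% |
| 16 (with extras) | 26 | 16/26 = 62% |

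No reading at the level of the whole period closes the gap. At two doses a day, 14 syringes last 14/2 = 7 days and 16 last 16/2 = 8 days. The rows with 16 syringes assume that the extras include syringes. The sentence places the extras after the albuterol containers and does not say whether they cover syringes, albuterol or both.

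**Step 3. Find which reading gives 14**

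- One week of the stated regimen: 1 x 2 x 7 = 14.
- One dose a day for 14 days: 1 x 1 x 14 = 14. This conflicts with every statement of the daily frequency.

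The first reading fits the 7-day supplies in Section 7.5. Two such supplies give 2 x 14 = 28, or 2 x 16 = 32 if each carries two extras. That total matches the regimen in the synopsis, 4.1 and 7.4.1, but not the wording of 7.3.2, which calls 14 the total for the period.

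**Step 4. Product name**

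Table 1 gives 100 mg/mL, which is 10%. The synopsis and Sections 4.1, 7.1 and 7.3 also state 10%. The strength is therefore consistent, and only the trade-name suffix differs between 7.3.1 and 14.3.

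**The case against.** The best defence is that the procedures already describe a full two-week supply. Sections 7.5 and 7.6 and the Visit 5 and Visit 9 lists all provide a second seven days of drug. Section 7.4 has the compounding pharmacy deliver against prescriptions as needed. Nothing says that Section 7.3.2 sets the order quantity. This stands, and it limits what can be concluded about consequences.

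A reader might draw three stronger conclusions that the documents do not support.

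- **That participants run out at mid-period.** The visit lists provide a second supply at exactly that point, so an actual shortage is not shown.
- **That even perfect use would fail the 70% adherence rule, because 50% and 57% are both below 70%.** Section 7.6 and the Visit 5 list apply that rule after the first seven days of treatment. The regimen then implies 2 x 7 = 14 doses, and a participant who used 14 syringes would score 14/14 = 100%. The comparison mixes a 28-dose denominator with a one-week check. No adherence formula is written down, but the timing of the check points to one week.
- **That the two product names mean two strengths.** The strength is 10% throughout, so the mismatch is a labelling slip.

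The defence does not rescue the sentence itself. Section 7.3.2 says both that 14 is a total and that it is for each treatment period, so it cannot be read as a weekly count without changing its words.

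**Conclusion.** Section 7.3.2 contradicts the rest of the protocol as written. Its period total is 14 of each item, against 28 implied by the synopsis, 4.1 and 7.4.1. That is 50% of the stated regimen, or at most 57% of the 28 doses if both extras are syringes. The count of 28 rests only on one syringe and one albuterol unit per dose, two doses a day and 14 days, all stated in the protocol.

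A weekly count labelled as a period total is the likeliest explanation. That is an inference from the match with one 7-day supply, not something the documents say. The finding is about the text and does not show that any participant was under-supplied. It does not touch the sample size or the analysis method. The product-name mismatch is minor and separate.

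**What to change.** The sponsor should reconcile Section 7.3.2 with the synopsis (test and control products), Sections 4.1, 7.4.1, 7.5 and 7.6, and the Visit 5 and Visit 9 lists. The syringe and albuterol counts per dispensing visit and per treatment period should then agree wherever they appear. The text should also say:

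- whether the two extras are syringes, albuterol units or both, and whether they are per dispensing visit or per period;
- whether the two supervised doses come out of the stated count.

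Separately, the product name in Section 7.3.1 should be reconciled with Section 14.3 and with the concentration in Table 1.

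This review takes no position on which count, regimen or product name is right. The cost is a protocol clarification and a check of the pharmacy documents against it, best done before drug is ordered.

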## 7.4 Supply of Study Drug at the Site

Study drug will be supplied to both sites by Mariner Advanced Pharmacy Corp (MAPRx). MAPRx is a professional 503(a) patient-centered compounding pharmacy which prepares sterile and nonsterile drug preparations compliant with United States Pharmacopeia standards and the California State Board of Pharmacy.

The study medication will be supplied by MAPRx and delivered as needed per prescription. MAPRx can guarantee medication delivery to the study site within 1-2 business days of submitting a prescription via MAPRx's secured dashboard webportal.

### 7.4.1 Dosage/Dosage Regimen

During each treatment period participants will nebulize one syringe of study drug and one unit dose container of albuterol using a portable nebulizer. Participants will be instructed to take two doses per day, spaced at approximately 8-12 hour intervals. No adjustments will be made based on weight or age.

### 7.4.2 Dispensing

Study medication will be dispensed by either, the study coordinator, study nurse or physician and only after observation of the administration of the first two doses of each treatment period.

### 7.4.3 Administration Instructions

#### Charge Check

1. Wash hands prior to preparing each treatment.
2. Use a clean nebulizer.
3. Check the battery level by pressing the on/off button on the handset
  - a. If the LED is **SOLID GREEN** the battery is charged
  - b. If the LED is **SOLID AMBER**, there is enough charge for at least one more treatment  
\*Please charge your nebulizer after your treatment
  - c. If the LED **FLASHES AMBER** and then switches off there is not enough charge to take a treatment  
\*Please charge your nebulizer before treatment
  - d. If the LED does not illuminate, please refer to the troubleshooting sections of the manual and call the study coordinator

#### Nebulizer Assembly

1. Empty the contents of one-unit dose container labeled “albuterol” into the medication chamber with the green lid
2. Empty the contents of one syringe into the medication chamber
3. Close the lid to the medication chamber

#### Treatment

1. Hold the handset in your hand and place the mouthpiece between your teeth with your lips sealed around it.
2. Press the on/off button on the handset to switch the nebulizer on and begin nebulization and breathe normally through your mouth
3. Ensure aerosol is coming out of the mouthpiece assembly
4. Keep the nebulizer in an upright position during the course of the treatment. This prevents spilling and promotes nebulization
5. If you need to take a rest, press the on/off button to stop your treatment. To continue your treatment press the on/off button again
6. Your treatment is finished when the nebulizer beeps and the LED flashes. The device will turn off automatically
7. Check the medication chamber for residual medication. If there are more than a few drops remaining, press the on/off button again to continue your treatment

#### After each use

1. Press the mouthpiece assembly release button to separate the mouthpiece assembly from the handset.
2. Rinse the mouthpiece assembly thoroughly under running tap water
3. Shake off excess water and allow to air dry fully before storing

### **Daily cleaning**

1. Once per day, wash the mouthpiece assembly by hand in a bowl of warm soapy water (liquid dish soap) for 2 minutes
2. Rinse the mouthpiece assembly thoroughly under running tap water
3. Shake off excess water and allow to air dry fully before storing

### **Weekly disinfection**

1. Prior to disinfection, ensure all parts are visibly clean and free from dirt/debris
2. Ensure the medication chamber lid is open and boil the mouthpiece assembly in water deep enough to prevent mouthpiece from touching the bottom for 10 minutes
3. Shake off excess water and allow to air dry fully before storing

## **7.5 Supply of Study Drug at the Site**

Study drug supply will be maintained by MAPRx and will be supplied on a per participant basis. 7-day study drug supplies will be delivered to the clinical site within 48 hours of study visit corresponding to the start of week one of the treatment period and week two of the treatment period.

### **7.5.1 Storage**

Study drug should will be shipped and stored by the study site at refrigeration temperature, 2 to 8°C (36 to 46°F). If the temperature of study drug storage in the clinic/pharmacy exceeds or falls below this range, this should be reported to the Sponsor or designee and captured as a deviation. Participants will be instructed to store the medication in original packaging in the refrigerator according to the instructions outlined on the Drug Administration Instructions.

## **7.6 Study Drug Accountability**

An accurate and current accounting of the dispensing and return of study drug for each participant will be maintained on an ongoing basis by a member of the study site staff.

### Measures of Treatment Compliance:

Participants will be asked to keep a patient diary noting the day and date they take their study drug, whether they cotreat with albuterol and any adverse events. They will be asked to bring their patient diary to each study visit along with all used and unused study drug containers. After the first 7 days of treatment, subjects will be asked to return to the research center for a follow-up visit to measure adherence and to obtain the last 7 days of study drug. If the subject's adherence is less than 70%, during the first treatment period subjects will be terminated and will not receive any additional intervention or follow-up.

## 8 STUDY PROCEDURES AND GUIDELINES

A Schedule of Events representing the required testing procedures to be performed for the duration of the study is diagrammed in Appendix A.

Prior to conducting any study-related activities, written informed consent and the Health Insurance Portability and Accountability Act (HIPAA) authorization must be signed and dated by the participant.

### 8.1 Clinical Assessments

#### 8.1.1 Concomitant Medications

All concomitant medication and concurrent therapies will be documented at Baseline/Screening and at early termination when applicable. Dose, route, unit frequency of administration, and indication for administration and dates of medication will be captured.

#### 8.1.2 Medication Withholding

Bronchodilator reversibility will be used to establish eligibility at Visit 2a and will also be performed at visits 3-10. Since some asthma medications can blunt the response to bronchodilators, we may ask that participants withhold these medications according to the guidance provided in Table 2.

**Table 2. Medication Withholding Parameters**

Medication	Withholding period
Leukotriene modifiers	24h
Ultra-long-acting bronchodilators (indacaterol)	24h
Long-acting muscarinic antagonists ( tiotropium , glycopyrronium , umeclidinium )	24h
Long-acting muscarinic antagonists ( aclidinium )	12h
Long-acting beta-agonists	12h
Theophylline	12h
Short-acting anticholinergic	6h
Short-acting beta-agonists	4h

Participants will be evaluated at visit 1, without any medication holds, to establish the safety of withholding asthma medications. If a study clinician feels the participant is not clinically stable enough to withhold medications, they may shorten the guidance (with appropriate documentation on the Visit 1 CRF Physician Attestation section) or they may excuse the participant from some or all of the medication withholds.

Participants are reminded of these medication holds by phone or email 24 hours prior to their medication withholding visits and instructed to resume all medications should symptoms develop in the period prior to the visit.

Associated risks of medication withholding include a worsening of asthma control or asthma exacerbation. To mitigate these risks, participants are given clear instruction to resume asthma medications if symptoms arise.

### **8.1.3 Food & Beverage Withholding**

Participants are asked to withhold eating for our hour prior to sputum induction (visits 2, 6, 7 and 10) because recently digested food can contaminate sputum samples. Participants are also asked to withhold caffeine and alcohol containing products for 6 hours prior to all study visits as these substances can influence lung function values.

### **8.1.4 Demographics**

Demographic information (date of birth, gender, race) will be recorded at Screening.

### **8.1.5 Medical History**

Relevant medical history, including history of current disease, other pertinent respiratory history, and information regarding underlying diseases will be recorded at Screening.

Associated risks include discomfort evoked with some of the questions asked. To minimize risk, participants will be informed that they can defer answering any questions that make them feel uncomfortable.

### **8.1.6 Physical Examination**

A complete physical examination will be performed by either the investigator or a study clinician (MD, NP, RN, and PA) at visit 1. New abnormal physical exam findings must be documented and will be followed by a physician or other qualified staff at the next scheduled visit. Abbreviated physical exams may be performed as needed at visits 2-10.

### **8.1.7 Vital Signs**

Body temperature, blood pressure, pulse, and respirations will be performed after resting for 5 minutes at all study visits.

### **8.1.8 Oximetry**

Oximetry will be measured on room air with the participant at rest at all study visits.

### **8.1.9 Spirometry**

Spirometry will be performed at visits 1-10 in accordance with the current American Thoracic Society recommendations for the performance and interpretation of tests.

Associated risks include the following:

- Likely (>10%)
  - Shortness of breath or cough during the six-second exhalation part.

- Less Likely (<5%)
  - Wheezing and chest tightness.
- Rare but serious (<1%)
  - Syncope

In an effort to minimize risk to participants will be seated during the procedure to reduce any injury should a participant become dizzy and fall. Coordinators will have albuterol available to administer to participants who develop wheeze or shortness of breath following spirometry.

#### **8.1.10 Post-Bronchodilator Reversibility/Maximal Reversibility**

Spirometry will be repeated 15 minutes following the administration of four to eight puffs of albuterol to assess bronchodilator reversibility. Maximal bronchodilation will be performed at Visit 2a. Post-bronchodilator reversibility will be performed at Visits 3-10.

Associated risks include the following:

- Likely (>10%): Transient tachycardia, tremor, feeling nervous, rhinitis, pharyngitis, and nausea
- Less Likely (<5%): Headache, cough, upper respiratory infection
- Rare but serious (<1%): Chest pain, atrial fibrillation, hypertension, hypotension, diabetic ketoacidosis, hyperglycemia, hypersensitivity reactions, paradoxical bronchospasm

Given that the study population is made up of individuals with moderate-to-severe asthma, and that albuterol is a standard of care treatment for asthma, it is unlikely that participants will experience any of the side effects described above. However, if a potential participant describes previous sensitivity or side effects to treatment with albuterol, they will be excluded from participation for safety. Furthermore, albuterol will only be administered after a physician-administered history and physical, to ensure that it is okay for the participant to receive albuterol.

#### **8.1.11 Methacholine Challenge Testing**

Methacholine challenge testing will be done according to the steps laid out in the UCSF Airway Clinical Research Center Methacholine Challenge Test Manual of Procedures or the University of California, Davis Pulmonary Services Laboratory standard protocol. Only participants that are unable to achieve 12% improvement in FEV1% following administration of 4 puffs of albuterol and who have a baseline FEV1 >50% predicted will undergo methacholine challenge testing.

Associated risks include the following:

- Likely (>20%)
  - Shortness of breath.
- Less Likely (< 20%)
  - Wheezing, tightness, or cough.

- Rare but serious (< 1%)
  - Rarely, patients may have severe bronchoconstriction during or following methacholine challenge.

Additionally, methacholine has been shown to increase tone of the uterus, which could lead to preterm labor, in pregnant laboratory animals; there are no human studies to verify this effect during human pregnancy. However, because of this, methacholine has been placed in FDA category C, meaning that exposure during pregnancy should be avoided. As such, pregnant women or women of reproductive age who are unwilling to practice pregnancy prevention strategies will be excluded from participation.

In an effort to minimize risk to participants, only those participants with a pre-diluent FEV1 of >50% predicted will undergo the methacholine testing, and only in the instance that they are not able to show 12% or greater improvement in FEV1 following bronchodilator administration. A study physician will be available during the challenge. Participants will not be discharged until their FEV1 is within 10% of their prediluent FEV1. Medications and personnel will be available to manage and treat bronchoconstriction.

